3.1.5. Follow-up Period

During the follow-up period, subjects will continue to be monitored for safety. Subjects whose most recent 24-hr UFC is \leq ULN will have a follow-up visit (Visit F1/End-of-Study, EoS; this is the same as the end of trial) at the study site 2 weeks after their ET/EoT visit. Subjects whose most recent 24-hr UFC is $>$ ULN will have a follow-up telephone visit instead of a study site visit.

- Study Days 86-98: If the Day 79 24-hr UFC is \leq ULN, a follow-up visit (Visit F1) at the study site will be scheduled for Day 98, 2 weeks after the EoT visit. This visit will consist largely of safety assessments. Subjects whose Day 84 24-hr UFC is also \leq ULN will begin a 24-hr urine collection on Day 92 and finish on Day 93. If the Day 79, Day 84 or Day 92 24-hr UFC is $>$ ULN, a telephone visit will be conducted on Day 98 instead of a study site visit (in case of discrepant results, the latest result should be used). If the Day 92 24-hr UFC result is unknown at the time the Day 98 visit is due, the subject will proceed with having the Day 98 visit at the study site.
- Subjects whose Day 92 24-hr UFC is \leq ULN should continue to be followed up and have morning serum ACTH and 24-hr UFC assessed every 2-4 weeks until their 24-hr UFC is $>$ ULN or until the Investigator and the Medical Monitor agree that the subject is stable.

Throughout the course of the study, safety evaluations will include assessment of AEs, concomitant medications, clinical laboratory tests, vital signs, physical examinations (PEs) and 12-lead electrocardiograms (ECGs).

A detailed schedule of study assessments is presented in [Appendix 1](#).

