5.11. Concomitant Medications

Use of concomitant medications should be kept to a minimum during the study. However, if concomitant medications are considered necessary for the subject's welfare and are unlikely to interfere with the investigational product, they may be given at the discretion of the Investigator. During the study (i.e., from screening (Visit S1) until the end of the study/end of trial (Visit F1)), any medication given other than the study drug (including blood transfusions and parenteral fluids) is to be considered a concomitant medication and must be documented on the eCRF. See Section 6.5 for additional details regarding documentation of prior and concomitant medications.

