6.9. Adverse Events, Serious Adverse Events and Reporting

6.9.1. Definition of Adverse Event, Adverse Drug Reaction and Unexpected Adverse Drug Reaction

Adverse Event (AE): Any untoward medical occurrence associated with the use of a drug in humans, whether or not considered drug-related.

- All AEs, regardless of relationship to study drug, should be collected beginning from the time the subject signs the study consent until the last study visit or 30 days after the last dose of study drug, whichever is later. (Any SAE judged by the Investigator to be related to the study treatment should be reported to the Sponsor regardless of the length of time that has passed since study completion.) AEs in study subjects include any change in the subject's condition. This includes symptoms, physical findings, or clinical syndromes.
- Wherever possible, a specific disease or syndrome, rather than individual associated signs and symptoms should be identified by the Investigator and recorded. However, if an observed or reported sign or symptom is not considered a component of a specific disease or syndrome by the Investigator, it should be recorded as a separate AE. Additionally, the condition that led to a medical or surgical procedure (e.g., surgery, endoscopy, tooth extraction, or transfusion) should be recorded as an AE, not the procedure. Any medical condition already present at screening should not be reported as an AE unless the medical condition or signs or symptoms present at baseline worsens in severity or seriousness at any time during the study. Clinically significant examination (e.g. electrocardiogram) findings that are detected during the study or are present at screening and worsen during the study should be reported as an AE.
- An abnormal laboratory value may be considered an AE if the identified laboratory abnormality leads to any type of intervention, whether prescribed in the protocol or not. It is up to the Investigator to determine whether an abnormal laboratory value constitutes an AE. If an abnormal laboratory value is caused by a disease process, the disease process and not the laboratory abnormality should be listed as the AE (e.g., if new onset viral hepatitis is causing elevated ALT, hepatitis and not the elevated ALT should be listed as the AE).

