6.9.4.2. Reporting SAEs – Procedure for Investigators

Initial Reports

SAEs, regardless of causality assessment, must be collected beginning from the time the subject signs the study consent until the last study visit or 30 days after the last dose of study drug, whichever is longer. All SAEs must be reported to Medpace Clinical Safety **within 24 hrs** of the knowledge of the occurrence (this refers to any adverse event that meets any of the aforementioned seriousness criteria). Any SAE judged by the Investigator to be related to the study treatment should be reported to the Sponsor regardless of the length of time that has passed since study completion.

To report the SAE, complete the SAE form electronically in the electronic data capture (EDC) system for the study. When the form is completed, Medpace Safety personnel will be notified electronically and will retrieve the form. If the event meets seriousness criteria and it is not possible to access the EDC system, send an email to Medpace Safety at [contact] or call the Medpace SAE hotline (phone number listed below) and fax or email the completed paper SAE form to Medpace (fax number/email address listed below) within 24 hrs of awareness. When the EDC system becomes available, the SAE information must be entered within 24 hrs of the system becoming available.

It is very important that the SAE electronic case report form be filled out as completely as possible at the time of the initial report, including if possible the Investigator's assessment of causality. The minimum information needed for making a preliminary SAE report is the protocol number, the subject ID, an adverse event term and the name of the person reporting the information to the Sponsor. Preliminary SAE reports should be followed as soon as possible by detailed descriptions including copies of hospital case reports, autopsy reports and other documents requested by the Sponsor (see Follow-up Reports, below).

Medpace Clinical Safety Contact Information:

Medpace SAE hotline – USA:
[contact], [name] **or** [contact], [name]
[contact] **or** [contact]
e-mail: [contact]

Medpace SAE hotline – Europe:
[contact]
[contact]
e-mail: [contact]

Follow-up Reports

All AEs and SAEs must be followed to resolution or, if resolution is unlikely, to stabilization.

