7.5.2. Follow-up, Visit F1 (End-of-Study (EoS); End of Trial)

The target study day for the follow-up (EoS; end-of-trial) visit is 13 days after Visit R3/A3/ET. Only subjects whose most recent available 24-hr UFC is \leq ULN need to have a follow-up visit at the study site. All other subjects should be followed up via telephone to assess for new AEs and concomitant medications. Subjects who have ongoing AEs should be followed up as appropriate.

Subjects whose Day 92 24-hr UFC is \leq ULN should continue to be followed up and have morning serum ACTH and 24-hr UFC assessed every 2-4 weeks until their 24-hr UFC is $>$ ULN or until the Investigator and the Medical Monitor agree that the subject is stable.

At Visit F1 (EoS; end of trial), appropriate study site personnel should:

- Record adverse events and update medications.
- Record vital signs and weight.
- Perform a brief PE, with particular attention to assessing the subject for adrenal insufficiency.
- Collect blood samples for hematology, chemistry and hormones (11-DOC, 17-OHP, A, A4, ACTH, cortisol, DHEA, DHEAS, free T, P, renin, SHBG and total T).

- All blood hormone collections should be performed between 6-10 AM (06:00-10:00), as close to 8 AM (08:00) as practicable.
- Subjects need to be in a seated position for at least 15 minutes prior to collection of blood hormone levels so that renin and aldosterone levels are stable.
- If the subject is a woman of childbearing potential, collect a urine sample and perform a urine pregnancy test (preferred; or submit a serum or urine sample to a laboratory for pregnancy testing if required by your institution/IRB/EC).
- If the subject's most recent available 24-hr UFC result is \leq ULN, then:
 - Provide instructions regarding a 24-hr urine sample to be collected at home within 2-4 weeks after the previous sample.
 - Schedule the next study visit (unscheduled follow-up).
- At the completion of Visit F1 and all follow-ups, once the 24-hr UFC is $>$ ULN, discharge the subject from the study.

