ⁱ TWO early morning (30-45 minutes after awakening for the day) and TWO late night (10 PM - 12 AM; 22:00-00:00) saliva collections for salivary cortisol should be performed during the screening period within 28 days of enrollment into the open-label dose-escalation period and results reviewed for eligibility prior to enrollment. Subjects who require wash-out of medications should perform these collections AFTER wash-out. A visiting nurse may assist with processing and shipping the Screening and Day 41, 42, 50, 51, 64 (if applicable), 65 (if applicable), and 79 saliva collections to the central laboratory; or the subject may submit these to the study site for shipping to the central laboratory, per subject preference (all other collections should be brought by the subject to the next visit at the study site).

^j For subjects in the double-blind randomized withdrawal period, if the mean Day 64/65 24-hr UFC result is available prior to or at the time of R2, study completion assessment will be performed: if subjects are found to have met criteria for completing the study (i.e., 24-hr UFC is $>$ 1.3 \times ULN and has also increased by $>$ 50% relative to the mean Day 50/51 24-hr UFC), R3 will be conducted, rather than R2 (i.e., the subject will skip R2). If the mean Day 64/65 24-hr UFC does not meet criteria for completing the study, or the result is not available at the time of R2, the subject will proceed with R2.

^k Adverse events will be collected from the time the subject signs the informed consent form until the last study visit or 30 days after the last dose of study drug, whichever is later.

11-DOC, 11-deoxycorticosterone; 17-OHP, 17-hydroxyprogesterone; A, aldosterone; A4, androstenedione; ACTH, adrenocorticotrophic hormone; aPTT, activated partial thromboplastin time; demog, demographics; DHEA, dehydroepiandrosterone; DHEAS, dehydroepiandrosterone sulfate; ECG, electrocardiogram; ET, Early Termination; excl, exclusion; HbA1c, hemoglobin A1c; HBsAg, hepatitis B surface antigen; HCV, hepatitis C virus; HIV, human immunodeficiency virus; incl, inclusion; INR, international normalized ratio; P, progesterone; PE, physical examination; PK, pharmacokinetic(s) (samples); PT, prothrombin time; SHBG, sex hormone binding globulin; T, testosterone; tel, telephone visit; UFC, urinary free cortisol; ULN, upper limit of normal

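### AE and SAE collection runs to at least 30 days after the last dose, but subjects with UFC above ULN have their last scheduled contact about 14 days after it, and medication recording stops there too

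*Protocol*

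**What the plan says.** The collection period is stated three times. Section 6.9.1 sets it for all AEs as "until the last study visit or 30 days after the last dose of study drug, whichever is later". Section 6.9.4.2 sets it for SAEs as "until the last study visit or 30 days after the last dose of study drug, whichever is longer". Footnote k to the Appendix 1 schedule repeats the AE rule. Thirty days after the last dose is therefore a minimum.

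The contacts come from section 7. No study drug is taken on the morning of R3 or A3, so the last dose is expected the evening before (sections 7.3.3, 7.3.4, 7.4.3, 7.4.4). Section 7.5.2 then says: "The target study day for the follow-up (EoS; end-of-trial) visit is 13 days after Visit R3/A3/ET". Only subjects whose latest UFC is at or below ULN attend the site. For the rest: "All other subjects should be followed up via telephone to assess for new AEs and concomitant medications". Tables 7 and 8 have no column after Day 98.

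Subjects whose Day 92 UFC is at or below ULN have further assessments every 2 to 4 weeks. Concomitant medication is recorded "from screening (Visit S1) until the end of the study/end of trial (Visit F1") under section 5.11, and section 6.5 gives the same end point.

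**The concern.** A site that carries out section 7 as written makes its last enquiry about AEs and medications well before the protocol's own collection period closes. After that call, a subject above ULN has no planned contact. A new AE, or an SAE not judged related, enters the database only by spontaneous report. A drug given to treat such an event, or a new Cushing's agent started after F1, falls outside the recording period by rule. Sections 7.3.4 and 7.4.4 allow these same subjects to start another agent after R3/A3, so medication changes in this interval are likely to be of interest.

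What is at stake is the completeness of safety data. It has some weight because this is the first study of ATR-101 in Cushing's syndrome (section 1.2.2), there is no DSMB (section 10.8), and section 3.8 relies on the frequency of visits and laboratory tests in place of stopping criteria.

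**Working it through.** Inputs, all from the protocol:

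- R3/A3 on Day 85 and F1 on Day 98 (Tables 7 and 8)
- last dose the evening before R3/A3, so Day 84 (sections 7.3.4, 7.4.4)
- F1 window ±7 days (sections 6.1 and 7)
- collection period at least 30 days after the last dose (sections 6.9.1 and 6.9.4.2)

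**The plan's own figures.** F1 − R3/A3 = 98 − 85 = 13 days, as section 7.5.2 states. Eight weeks of screening plus 98/7 = 14 weeks gives 22 weeks, the upper duration in section 3.3. So the planned duration ends at F1, not at day 30 after the last dose.

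**Gap for subjects above ULN, full course.**

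- F1 − last dose = 98 − 84 = 14 days; with the window, 7 to 21 days. F1 on schedule never reaches day 30.
- End of the collection period = 84 + 30 = Day 114.
- Gap = 114 − 98 = 16 days at target; 114 − 105 = 9 if F1 is a week late; 114 − 91 = 23 if a week early.

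**Other exit times.** Let V be the day of R3/A3. The last dose is V − 1, the period ends at V + 29 and F1 is V + 13, so the gap is 16 days whatever V is. A subject who completes early with R3 on Day 71 has the last dose on Day 70, F1 on Day 84 and the period ending on Day 100: again 16 days. If an early-termination visit takes place d days after the last dose, the gap is 30 − d − 13 = 17 − d: 16 days if d = 1, none if d is 17 or more.

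**Subjects at or below ULN.** The first further sample follows the Day 92 sample by 14 to 28 days: Days 106 to 120. At target dates this falls at most 114 − 106 = 8 days short of Day 114. If the Day 92 sample is taken a week early, on Day 85, the first further sample can fall on Day 99, which is 114 − 99 = 15 days short.

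**Placebo subjects.** Their last active dose is Day 56. F1 is 98 − 56 = 42 days later after a full course, or 84 − 56 = 28 days later if they complete early at Day 71.

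**The case against.** The strongest reply is that nothing here conflicts. Sections 6.9.1 and 6.9.4.2 set a collection period; section 7 sets contacts. Allowing for whichever date is later already accepts that the last visit may come before day 30, and footnote k attaches the 30-day duty to the AE row of the schedule. That stands. A reader might infer a contradiction, but the documents show only a period with no planned enquiry in its second half.

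A reader might also infer that section 7.5.2 discharges telephone subjects at the call. It does not. The discharge sentence belongs to the list for the on-site F1 visit and refers to completion of F1 and all follow-ups. No text tells a site to stop collecting.

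Nor do all early completers belong to this group. They qualify on the mean of the Day 64 and 65 values being above 1.3 × ULN, while the follow-up rule uses the latest single UFC. The two usually agree, but need not.

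Existing rules close part of the gap. Related SAEs are reportable at any time, ongoing AEs are followed, and medications started before F1 are recorded. For subjects at or below ULN, section 3.1.5 implies AE assessment at the extra visits: "Throughout the course of the study, safety evaluations will include assessment of AEs, concomitant medications". None of these asks a subject above ULN about new events after F1.

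Pregnancy is a weaker strand. Conceptions within 30 days of the last treatment are reportable under section 6.9.5, but on notification, and a call at day 30 would miss many late ones.

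**Conclusion.** The point holds as a modest improvement in safety ascertainment. For subjects above ULN at F1, 16 days of the 30-day period (9 to 23 across the F1 window) have no scheduled contact, and medication recording is over. Subjects at or below ULN are partly covered, with a shortfall of up to 8 days at target dates and up to 15 with the Day 92 window.

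These are days, not missed events. The protocol gives no event rate and does not say how many subjects will be above ULN at F1; anything from 0 to 16 is possible. The 16-day figure assumes that the last dose is taken the evening before R3/A3, and it shrinks if an early-termination visit comes later after the last dose. It would be wrong to read this as a between-arm bias or as a threat to the efficacy result; the documents support neither. For placebo subjects, already 28 to 42 days past active drug at F1, the gap matters little.

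**What to change.** Add to section 7.5.2 and Tables 7 and 8:

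> All subjects will be telephoned 30 days or more after the last dose of study drug to record new AEs, concomitant medications and, where applicable, any known pregnancy; a follow-up contact on or after that date may replace the call.

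Extend medication recording in sections 5.11 and 6.5 to that call. Apply it to every subject: it adds little for placebo subjects, but calling everyone protects the blind.

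Do not redefine the end of study. Sections 5.12 and 5.13 and inclusion criterion 6 tie prohibited medications, elective surgery and contraception to the duration of the study, so moving its end from about Day 98 to Day 114 would lengthen those restrictions by 16 days, including for subjects with uncontrolled cortisol. Keep F1 as the end-of-study visit, and state that the call is safety follow-up only and extends none of these restrictions.

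The cost is about 16 telephone calls, one per planned subject and fewer where a later contact replaces the call, plus a minor amendment. It adds no site visit or invasive procedure.

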6.9.2. Assessing Severity of Adverse Events

The assessment of severity must be provided by the Investigator and based on the Investigator's clinical judgement. Maximum severity should be assigned to one of the following categories:

- **Mild:** An AE that is easily tolerated by the subject, causing minimal discomfort and not interfering with everyday activities.
- **Moderate:** An AE that is sufficiently discomforting to interfere with normal everyday activities.
- **Severe:** An AE that prevents normal everyday activities.

An AE that is assessed as severe should not be confused with a serious AE (SAE). Refer to Section 6.9.4.1 for the definition of an SAE.

6.9.3. Assessing Relationship to Study Treatment

The Investigator will categorize each AE as to its potential relationship to study drug: **unrelated**, **unlikely related**, **possibly related**, **probably related** and **definitely related**. Items to be considered when assessing the relationship of an AE to the study treatment are as follows:

- Temporal relationship of the onset of the event to the initiation of the study treatment

- The course of the event, considering especially the effect of discontinuation of study treatment or reintroduction of study treatment, as applicable
- Whether the event is known to be associated with the study treatment or with other similar treatments
- The presence of risk factors in the study subject known to increase the occurrence of the event
- The presence of non-study treatment-related factors that are known to be associated with the occurrence of the event

The relationship categories of unrelated and unlikely related will be summarized for reporting purposes as **Not Related**. For Not Related events, the time course between the administration of study drug and the occurrence or worsening of the AE rules out a causal relationship with study drug, and another cause of the AE (concomitant drugs, therapies, complications, etc.) is suspected.

The relationship categories of possibly, probably and definitely related will be summarized for reporting purposes as **Related**. Only AEs thought to be caused by the study drug should be classified as “related to study drug.” For Related events, the time course between the administration of study drug and the occurrence or worsening of the adverse event is consistent with a causal relationship, and no other cause (concomitant drugs, therapies, complications, etc.) can be identified. The definition implies a reasonable possibility of a causal relationship between the event and the study drug. This means that there are facts (evidence) or arguments to suggest a causal relationship.

6.9.4. Serious Adverse Events

6.9.4.1. Definition of Serious Adverse Event

A serious adverse event (experience; SAE) or reaction is any untoward medical occurrence that:

- Results in death
- Is life-threatening (Note: The term “life-threatening” in the definition of “serious” refers to an event in which, in view of either the Investigator or Sponsor, the subject was at immediate risk of death at the time of the event; it does not refer to an event that hypothetically might have caused death if it were more severe.)
- Requires inpatient hospitalization or prolongation of an existing hospitalization

Note: Any hospital admission with at least one overnight stay will be considered an inpatient hospitalization. An emergency room visit without hospital admission will not be recorded as an SAE under this criterion, nor will hospitalization for a procedure scheduled or planned before signing of informed consent. However, unexpected complications and/or prolongation of hospitalization that occur during elective surgery should be recorded as AEs and assessed for seriousness.

The following hospitalizations are not considered to be SAEs because there is no “AE” (i.e., no untoward medical occurrence) associated with the hospitalization:

- Hospitalizations for respite/hospice care
- Hospitalization planned prior to informed consent (where the condition requiring the hospitalization has not changed post study drug administration)
- Results in persistent or significant incapacity or substantial disruption of the ability to conduct normal life functions
- Is a congenital anomaly/birth defect, or
- Is determined to be an important medical event (at the discretion of the Investigator)

Note: Important medical events that may not result in death, be life-threatening, or require hospitalization may be considered serious when, based upon appropriate medical judgment, they may jeopardize the subject and may require medical or surgical intervention to prevent one of the other outcomes listed in the SAE definition. Examples of such medical events include allergic bronchospasm requiring intensive treatment in an emergency room or at home, blood dyscrasias or convulsions that do not result in inpatient hospitalization, or the development of drug dependency or drug abuse.

